10.1.1 Part A: Combination Comparison of DFS

The combination comparison sample size is driven by the comparison of DFS between participants randomized to receive nivolumab + ipilimumab versus placebo. Approximately 800 participants will be randomized to the nivolumab + ipilimumab and placebo treatment arms in a 1:1 ratio with DFS medians of 111 and 72 months, respectively, rendering a 62-month study. Note the invocation of revprot03 will initiate the 1:1:2 (i.e. nivolumab + ipilimumab, placebo, nivolumab) randomization (see next section on Monotherapy Comparison of DFS).

Approximately 232 events among the approximately 800 contemporaneously randomized 1:1 participants are expected, ensuring 90% power to detect an average hazard ratio of 0.65 with an overall type I error of 0.05 (two-sided). The number of events and power were calculated assuming an exponential distribution and a delayed treatment effect of 3 months. This design yields a minimal HR of 0.764 ($P < 0.041$) when adjusting for interim analyses using Lan-DeMets alpha spending function.

Given accrual rates of 22 participants per month on average for the entire enrollment period, it is estimated that accrual of 800 participants (ie, 400 participants in each arm) will take approximately 36 months; it will take an additional approximately 26 months to observe the required number of events for the final DFS analysis.

There is 1 planned interim analysis of DFS. Stopping boundaries at the interim analyses will be derived based on the exact number of events using Lan-DeMets alpha spending function with O'Brien-Fleming boundaries. The DFS interim analysis is expected to occur at approximately 56 months when approximately 204 events are expected to have occurred. This will provide 83% power to detect an overall interim DFS HR of 0.743 ($P < 0.034$) at the pre-specified alpha level using the Lan-DeMets alpha spending function.

In the event that Part B enrollment is still ongoing at the time of observing the required number of events for the interim analysis and target number of events needed for the final analysis is projected in a shorter time interval (approximately within 4 months), then the interim analysis of DFS will not be performed and only one final analysis of DFS will be conducted after observing approximately 227 DFS events (required number of events since there is no alpha spending for DFS interim analysis) among all randomized participants. The 227 events are expected to provide 90% power to detect a DFS HR of 0.65 at alpha 0.05 (two-sided).

Table 10.1.1-1 summarizes sample size design parameters and schedule of primary endpoint analysis accounting for an interim and final analyses.

Table 10.1.1-1: Part A Summary of Sample Size Parameters and Schedule of Combination Analyses (with an Interim Analysis)

Primary Endpoint	DFS
Primary analysis population	All Randomized Participants
Accrual rate per month	22
Power	90%
Alpha	0.05 2-sided (0.034 at interim analysis, 0.041 at FA)
Hypothesized Median Control vs Experimental (Months)	72 vs 111
Hypothesized Hazard Ratio	0.65
Critical HR (HR at which a statistically significant difference would be observed) / Difference in median corresponding to a minimally significant effect size (Months)	0.764 / 22
Critical HR at interim analysis / Effect size (Months)	0.743 / 25
Expected events for interim analysis (percentage of target events)	204 (88%)
Timing of interim analysis from FPFV (Months)	56
Accrual Duration (Months)	36
Timing of final analysis (FA) from FPFV (Months)	62
Sample size ^a	800
Target number of events (Event Goal)	232

^a East version 5.4 was used for sample size / power computation

Table 10.1.1-2 summarizes sample size design parameters and schedule of primary endpoint analysis with one final analysis alone.

Table 10.1.1-2: Part A Summary of Sample Size Parameters and Schedule of Combination Analysis (without an Interim Analysis)

Primary Endpoint	DFS
Primary analysis population	All Randomized Participants
Accrual rate per month	22
Power	90%
Alpha	0.05
Hypothesized Median Control vs Experimental (Months)	72 vs 111
Hypothesized Hazard Ratio	0.65
Critical HR (HR at which a statistically significant difference would be observed) / Difference in median corresponding to a minimally significant effect size (Months)	0.771 / 21.4
Accrual Duration (Months)	36
Timing of final analysis (FA) from FPFV (Months)	61
Sample size ^a	800
Target number of events (Event Goal)	227

^a East version 5.4 was used for sample size / power computation

10.1.2 Part B: Monotherapy Comparison of DFS

The monotherapy comparison sample size is driven by the comparison of DFS between participants randomized to receive nivolumab versus placebo. Approximately 600 participants will be randomized to the nivolumab and placebo treatment arms in a 2:1 ratio (i.e. as part of the 1:1:2 ratio to nivolumab + ipilimumab, placebo, nivolumab) with DFS medians of 106 and 72 months, respectively, for a total accrual of approximately 56 months (20 additional months from the end of the combo test accrual).

Approximately 91 additional events are expected in the nivolumab arm for a total of 153 events among the 600 participants, ensuring 60% power to detect an average hazard ratio of 0.68 with an overall type I error of 0.05 (two-sided). Note that since the Part B participants are mutually exclusive from Part A participants no hierarchical testing for the primary endpoint is necessary (for more details, see [Section 10.3.4](#)). The number of events and power were calculated assuming an exponential distribution and a delayed treatment effect of 3 months. This design yields a minimal HR of 0.71 (P<0.043) when adjusting for interim analyses using Lan-DeMets alpha spending function.

Given accrual rates of 40 participants per month on average for the entire monotherapy enrollment period (1:1:2, thus 30 per month for only the monotherapy and placebo arms), it is estimated that

accrual of 600 participants (i.e., 400 participants to the nivolumab arm and 200 to the placebo arm) will take approximately 20 months; it will take an additional approximately 28 months (84 months from study initiation) to observe the required number of events for the final monotherapy DFS analysis.

There is 1 planned interim monotherapy analysis of DFS. Stopping boundaries at the interim monotherapy analysis will be derived based on the exact number of events using Lan-DeMets alpha spending function with O'Brien-Fleming boundaries. The DFS interim monotherapy analysis is expected to occur at approximately 76 months when approximately 122 events in the monotherapy and contemporaneous placebo arms are expected to have occurred. This will provide 40% power to detect an overall interim DFS HR of 0.65 ($p < 0.025$) at the pre-specified alpha level using the Lan-DeMets alpha spending function.

In the event that the target number of events for the interim analysis and final analysis are projected in a shorter time interval (approximately within 6 months), then the interim analysis of DFS will not be performed and only one final analysis of DFS will be conducted after observing approximately 149 DFS events among the randomized participants in the nivolumab and placebo arms (required number of events since there is no alpha spending for DFS interim analysis). The 149 events are expected to provide 60% power to detect a DFS HR of 0.68 at alpha 0.05 (two-sided).

Table 10.1.2-1 summarizes sample size design parameters and schedule of primary endpoint analyses planned in this study.

Table 10.1.2-1: Part B Summary of Sample Size Parameters and Schedule of Monotherapy Analyses (with an Interim Analysis)

Primary Endpoint	DFS
Primary analysis population	All Randomized Participants in Nivolumab and Placebo Arms
Accrual rate per month	40 (or 30 2:1 to N and P)
Power	60%
Alpha	0.05 2-sided (0.025 at mono interim analysis and 0.043 at mono final analysis)
Hypothesized Median Control vs Experimental (Months)	72 vs 106
Hypothesized Hazard Ratio	0.68
Critical HR (HR at which a statistically significant difference would be observed) / Difference in median corresponding to a minimally significant effect size (Months)	0.71 / 29
Critical HR at mono interim analysis / Effect size (Months)	0.65 / 39
Expected events for mono interim analysis (percentage of target events)	122 (80%)
Timing of mono interim analysis from FPFV (Months)	76

Table 10.1.2-1: Part B Summary of Sample Size Parameters and Schedule of Monotherapy Analyses (with an Interim Analysis)

Primary Endpoint	DFS
Accrual Duration (Months)	20
Timing of final analysis (FA for mono) from FPFV (Months)	84
Sample size ^a	600
Target number of events (Event Goal)	153

^a East version 5.4 was used for sample size / power computation

Table 10.1.2-2 summarizes sample size design parameters and schedule of primary endpoint analysis with one final analysis alone.

Table 10.1.2-2: Part B Summary of Sample Size Parameters and Schedule of Monotherapy Analyses (without an Interim Analysis)

Primary Endpoint	DFS
Primary analysis population	All Randomized Participants in Nivolumab and Placebo Arms
Accrual rate per month	40 (or 30 2:1 to N and P)
Power	60%
Alpha	0.05 2-sided
Hypothesized Median Control vs Experimental (Months)	72 vs 106
Hypothesized Hazard Ratio	0.68
Critical HR (HR at which a statistically significant difference would be observed) / Difference in median corresponding to a minimally significant effect size (Months)	0.71 / 29
Accrual Duration (Months)	20
Timing of final analysis (FA for mono) from FPFV (Months)	84
Sample size ^a	600
Target number of events (Event Goal)	149

^a East version 5.4 was used for sample size / power computation

10.1.3 Contribution of Components Analysis of DFS:

The contribution of components (CoC) will be assessed. The manner in which CoC will be measured is based on the hazard ratio and variance estimates computed for the contemporaneously randomized (approximately 200 vs 400) nivolumab + ipilimumab arm versus the nivolumab arm.

10.2 Populations for Analyses

For purposes of analysis, the following populations are defined:

Population	Description
All enrolled participants	
 All participants who signed an informed consent form and were registered into the IRT.
All enrolled Part A participants	
 All Part A participants who signed an informed consent form and were registered into the IRT.
All enrolled Part B participants	
 All Part B participants who signed an informed consent form and were registered into the IRT.
All treated participants	
 All participants who received at least 1 dose of study drug.
All treated Part A participants	
 All Part A participants who received at least 1 dose of study drug. This is the primary dataset for the Part A drug exposure and safety analysis.
All treated Part B participants	
 All Part B participants who received at least 1 dose of study drug. This is the primary dataset for the Part B drug exposure and safety analysis.
All randomized participants	
 All participants who were randomized to any treatment arm in the study. This population is considered the population for the combination overall survival analysis contingent on the primary DFS monotherapy analysis (for more details, see Section 10.3.4).
All randomized Part A participants	
 All Part A participants who were randomized to any treatment arm in the study. This population is considered for Part A as the primary efficacy analysis population. Analysis of demography, protocol deviations, baseline characteristics, efficacy analysis and outcome research analysis will be performed in this population.
All randomized Part B participants	
 All Part B participants who were randomized to any treatment arm in the study. This population is considered for Part B as the primary efficacy analysis population. Analysis of demography, protocol deviations, baseline characteristics, efficacy analysis and outcome research analysis will be performed in this population.
PK participants	
 All randomized participants with available serum time-concentration data.
PK Part A participants	
 All Part A randomized participants with available serum time-concentration data.
PK Part B participants	
 All Part B randomized participants with available serum time-concentration data.
Immunogenicity Evaluable Participants	
 Nivolumab ADA Evaluable Participants: all treated participants with baseline and at least 1 post-baseline pre-infusion nivolumab immunogenicity assessment. Ipilimumab ADA Evaluable Participants: all treated participants with baseline and at least 1 post-baseline pre-infusion ipilimumab immunogenicity assessment.

Population	Description
Immunogenicity Part A Evaluable Participants	
 • Nivolumab ADA Part A Evaluable Participants: all Part A treated participants with baseline and at least 1 post-baseline pre-infusion nivolumab immunogenicity assessment. • Ipilimumab ADA Part A Evaluable Participants: all Part A treated participants with baseline and at least 1 post-baseline pre-infusion ipilimumab immunogenicity assessment.
Immunogenicity Part B Evaluable Participants	
 • Nivolumab ADA Part B Evaluable Participants: all Part B treated participants with baseline and at least 1 post-baseline pre-infusion nivolumab immunogenicity assessment. • Ipilimumab ADA Part B Evaluable Participants: all Part B treated participants with baseline and at least 1 post-baseline pre-infusion ipilimumab immunogenicity assessment.
Biomarker participants:	All randomized participants with available biomarker data (PD-L1 expression status and other assays).
Biomarker Part A participants:	All Part A randomized participants with available biomarker data (PD-L1 expression status and other assays).
Biomarker Part B participants:	All Part B randomized participants with available biomarker data (PD-L1 expression status and other assays).

All analyses will be performed using the treatment arm as randomized (intent to treat), with the exception of dosing and safety, for which the treatment arm as received will be used:

- All randomized participants who take at least 1 dose of double-blind study treatment.
- Participants will be included in the treatment group they were randomized to, eg, data in this data set will be analyzed based on randomized treatment, except in the following cases:
 - If a participant received the same incorrect treatment throughout the study, then the participant will be analyzed based on the treatment received.
 - If a participant received study drug from more than 1 treatment group, and none of the administrations were consistent with the assigned randomized treatment group, then the participant will be analyzed based on the first treatment received.

10.3 Statistical Analyses

10.3.1 Efficacy Analyses

Endpoint	Statistical Analysis Methods
Primary	
The primary DFS analyses will be conducted using a 2-sided log-rank test stratified by pathological T Stage and N Stage status and type of nephrectomy at screening in randomized participants. The hazard ratio and corresponding 2-sided (1- α)% CI (adjusted for interim) will be estimated using a Cox proportional hazards model, with treatment group as a single covariate, stratified by the above factors. DFS curves, DFS medians with 95% CIs, and DFS rates at 6, 12, 18, 24, and 60 months with 95% CIs will be estimated using Kaplan-Meier methodology.
 
Note that upon completion of study enrollment, 2 of the 6 strata levels have less than 20 participants. To avoid unreliable estimates, the strata levels with partial and radical nephrectomy will be combined for stratified analysis purposes. In other words, stratified analysis will be conducted based only on 1 stratification factor (pathological T Stage and N Stage status).
 
For censoring rules, please refer to Table 10.3.1-1.

Secondary	
The secondary OS analysis will be conducted using a 2-sided log-rank test stratified by pathology status and histology at screening in randomized participants. The hazard ratio and corresponding 2-sided (1- α)% CI (adjusted for interim) will be estimated using a Cox proportional hazards model, with treatment arm as a single covariate, stratified by the above factors. OS curves, OS medians with 95% CIs and OS rates at 12, 24, 36, 48, and 60 months with 95% CIs will be estimated using Kaplan Meier methodology.
 
Note that upon completion of study enrollment, 2 of the 6 strata levels have less than 20 participants. To avoid unreliable estimates, the strata levels with partial and radical nephrectomy will be combined for stratified analysis purposes. In other words, stratified analysis will be conducted based only on 1 stratification factor (pathological T Stage and N Stage status).

Exploratory	Will be described in the statistical analysis plan finalized before database lock.

Censoring rules for the primary definition of DFS are presented in Table 10.3.1-1. Sensitivity analyses of DFS will be described in the statistical analysis plan.

Table 10.3.1-1: Censoring Scheme Used in Primary Definition of DFS

Situation	Date of Progression or Censoring	Outcome
Recurrence	Date of first recurrence	Event
Death from any cause without recurrence	Date of death	Event
No baseline disease assessment	Date of randomization	Censored
No on-study disease assessments and no death	Date of randomization	Censored
No recurrence and no death	Date of last evaluable disease assessment	Censored

Table 10.3.1-1: Censoring Scheme Used in Primary Definition of DFS

Situation	Date of Progression or Censoring	Outcome
New systemic anticancer therapy, tumor-directed radiotherapy, or tumor-directed surgery received without recurrence reported prior to or on the same day	Date of last evaluable disease assessment prior to or on the same date of initiation of subsequent therapy	Censored
Second non-RCC primary cancer reported without recurrence reported prior to or on the same day	Date of last evaluable disease assessment prior to or on the same date of diagnosis of secondary non-RCC primary cancer	Censored

10.3.2 Safety Analyses

Endpoint	Statistical Analysis Methods
Secondary	Safety analyses will be performed in all treated participants. Descriptive statistics of safety will be presented using NCI CTCAE version 4.0 by treatment group. All on-study AEs, treatment-related AEs, SAEs, and treatment-related SAEs up to 30 and 100 days of last dose of study therapy will be tabulated using worst grade per NCI CTCAE v 4.0 criteria by system organ class and preferred term. On-study lab parameters including hematology, chemistry, liver function, and renal function will be summarized using worst grade NCI CTCAE v 4.0 criteria.
Exploratory	Will be described in the statistical analysis plan, which will be finalized before database lock.

10.3.3 Other Analyses

10.3.3.1 Pharmacokinetic Analyses

The nivolumab and ipilimumab concentration versus time data obtained in this study will be combined with data from other studies in the clinical development program to develop a population PK model. This model will be used to evaluate the effects of intrinsic and extrinsic (if applicable) covariates on the PK of nivolumab and ipilimumab to determine measures of individual exposure (such as peak, trough and time-averaged concentration following a single dose or at steady state). Pharmacokinetic drug-drug interaction between nivolumab and ipilimumab will be studied by population PK approach as appropriate. Model determined exposures may be used for exposure -response analyses of selected efficacy and safety endpoints, if appropriate. The results of population PK, pharmacokinetic drug interaction and exposure response analyses will be reported separately, as needed.

10.3.3.2 Biomarker Analyses

Methodology for exploratory biomarker analyses will be described in the statistical analysis plan.

10.3.3.3 Outcomes Research Analyses

Descriptive summary statistics of quality of life assessments will be presented at baseline and each on-study time points unless otherwise specified. Mean changes from baseline for each of the 2 assessments and all associated subscores will be calculated for each treatment arm at each on-

study time point. More specifically, summary scores of the FKSI-19 subscale and total scores, the 9-item FKSI-DRS score, and the EQ-5D-3L utility index and VAS at baseline and on-study time points and the 95% CIs will be conducted. For the EQ-5D-3L utility index, the UK preference weightings will be analyzed.⁵⁵ In addition, participant compliance will be described per time point by the proportion of participants who filled out the QoL assessments over the numbers of participants known to be alive and eligible for assessment at these time points.

Additionally, t-tests will be conducted to evaluate the differences between nivolumab combined with ipilimumab versus placebo infusions treatment arms as well as the nivolumab versus placebo infusions treatment arms at each time point, and 95% CIs will also be presented.

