Myeloid Derived Suppressor Cells	X		X	Cytochex Tube. Prior to dosing. At Cycle 1 and 7.

Table 2-2: On-treatment Procedural Outline (CA209914) Part A and Part B

Procedure	Cycle 1 Day 1 (Nivolumab + Ipilimumab)	Cycles 2, 3, 5, 6, 8, 9, 11, & 12 Day 1 ^{a,b} Each Cycle = 2 weeks (Nivolumab alone)	Cycles 4, 7, & 10 Day 1, (Nivolumab + Ipilimumab)	Notes
SARS-CoV-2 Serology	X	X (C12D1 only)		Samples should be collected prior to dosing. Serum will be collected at C1D1 and C12D1 for all participants, and approximately 4 weeks after a suspected or confirmed SARS-CoV-2 infection to be used for potential future measurements of anti-SARS-CoV-2 serology (anti-SARS-CoV-2 total or immunoglobulin G (IgG) [see Section 9.8.9]). If a suspected or confirmed SARS-CoV-2 infection occurs within 4 weeks of the C1D1 or C12D1 time point, a single serum sample will be collected to satisfy the requirements for both the C1D1 or C12D1 and approximately 4 week after infection time points.
Efficacy Assessments				
Tumor Assessments	See Notes.			CT/MRI of the chest, abdomen, and pelvis. Assessment should be performed at Weeks 23, 36, and 52 (\pm 1 week) regardless of any dose delays. Use same imaging method as was used at screening/baseline. See Section 9.1.3 for additional details.
Patient-Reported Outcomes				
EQ-5D-3L	X	Cycles 3, 6, 9, and 12		Completed on Day 1 of Cycles 1, 3, 6, 9, and 12 prior to any study-related procedures.
FKSI-19	X ^c	Cycles 3, 6, 9 and 12		Completed on Day 1 of Cycles 1, 3, 6, 9, and 12 prior to any study-related procedures.

Table 2-2: On-treatment Procedural Outline (CA209914) Part A and Part B

Procedure	Cycle 1 Day 1 (Nivolumab + Ipilimumab)	Cycles 2, 3, 5, 6, 8, 9, 11, & 12 Day 1 ^{a,b} Each Cycle = 2 weeks (Nivolumab alone)	Cycles 4, 7, & 10 Day 1, (Nivolumab + Ipilimumab)	Notes
Drug Administration				
Randomize	X			Begins with call to Interactive Response Technology.
Administer nivolumab or placebo	X	X	X	Participants must begin study treatment within 3 calendar days of randomization.
Administer ipilimumab or placebo	X		X	Participants must begin study treatment within 3 calendar days of randomization.

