SARS-CoV-2 Serology		See Notes	Serum will be collected at Follow-up visit 2 only for all participants, and approximately 4 weeks after a suspected or confirmed SARS-CoV-2 infection to be used for potential future measurements of anti-SARS-CoV-2 serology (anti-SARS-CoV-2 total or IgG [see Section 9.8.9]). If a suspected or confirmed SARS-CoV-2 infection occurs within 4 weeks of the follow-up visit 2 time point, a single serum sample will be collected to satisfy the requirements for both the follow-up visit 2 and approximately 4 week after infection time points.

Table 2-3: Post-treatment Follow-up (CA209914) Part A and Part B

Procedure	Follow-Up Visit 1 and 2 ^a	Survival Follow-Up ^b	Notes
Tumor Biopsy	See Notes		Tumor biopsy collection at the time of recurrence is optional but highly encouraged.
Efficacy Assessments			
Tumor Assessments	See Notes		
 • Timing for scans should be based on date of first treatment, which is considered Week 1. Weeks 23, 36, and 52 (\pm 1 week window at each time point). • After Week 52 (first year), tumor assessments should occur every 6 months (\pm 2 week window) until Year 6. • Annually for Year 6 to Year 10 (\pm 2 week window). • Additional imaging of potential disease sites should be performed whenever disease recurrence or occurrence of a secondary malignancy is suspected. • Tumor assessments can be discontinued when recurrence has been confirmed by BICR. • Brain CT or MRI with contrast or bone imaging (confirmatory imaging in addition to bone imaging may be required) if clinically indicated. • See Section 9.1.3 for additional details.
Patient-Reported Outcomes			
EQ-5D-3L	X ^c (see Notes)	See Notes ^c	Perform at Follow-up 1 and 2, the first Survival Visit and at every other survival Follow-Up visit thereafter (Survival Follow-up visit 3, 5, 7, etc). ^c All patient-reported outcomes should be completed prior to study-related procedures, if possible.
FKSI-19	X ^c (see Notes)	See Notes ^c	

AE, Adverse event; ALP, alkaline phosphatase; ALT, alanine aminotransferase; AST, aspartate aminotransferase; BP, blood pressure; BUN, blood urea nitrogen; Ca, calcium; CBC, complete blood count; Cl, chloride; ctDNA, circulating tumor DNA; ECOG, Eastern Cooperative Oncology Group; FKSI-19, Functional Assessment of Cancer Therapy - Kidney Symptom Index; HR, heart rate; LDH, lactate dehydrogenase; K, potassium; Mg, magnesium, NA, sodium; SAE, serious

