
 To describe the safety and tolerability of nivolumab combined with ipilimumab and nivolumab monotherapy up to 30 and 100 days of last dose of study therapy. 	
 Safety and tolerability endpoint: type, incidence, severity (graded by the National Cancer Institute [NCI] Common Terminology Criteria for Adverse Events [CTCAE, Version 4.0], timing, seriousness, and relatedness, and laboratory abnormalities up to 30 and 100 days of last dose of study therapy in all treated participants.

Tertiary/Exploratory
 
 To assess PFS2 (progression after recurrence) in participants with localized renal cell carcinoma with a predominantly clear cell histology who have undergone a nephrectomy. To assess efficacy in the high and moderate risk subgroups. To assess disease-related symptoms in each arm based on the National Cancer Comprehensive Network (NCCN) Functional Assessment of Cancer Therapy - Kidney Symptom Index (FKSI-19). To assess changes in global health status in each treatment arm based on EuroQoL’s EQ-5D-3L. To correlate the primary tumor’s expression of PD-L1 with efficacy outcome (DFS, OS). Assess association between PD-L1 status and DFS and OS. To analyze biomarkers in tumor and peripheral blood to evaluate association with clinical efficacy or incidence of adverse events. 	
 PFS2. DFS and OS by the high and moderate risk subgroups. Change in FKSI-19 subscale and total scores relative to baseline. Change in scores from baseline in EQ-5D-3L in both the visual analog scale and the utility index. DFS and OS as described above. Selected biomarkers.

Table 4-1: Objectives and Endpoints

Objectives	Endpoints

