8 DISCONTINUATION CRITERIA

8.1 Discontinuation from Study Treatment

Participants MUST discontinue investigational product (and non-investigational product at the discretion of the investigator) for any of the following reasons:

- Participant's request to stop study treatment. Participants who request to discontinue study treatment will remain in the study and must continue to be followed for protocol specified follow-up procedures. The only exception to this is when a participant specifically withdraws consent for any further contact with him/her or persons previously authorized by participant to provide this information
- Any clinical AE, laboratory abnormality or intercurrent illness which, in the opinion of the investigator, indicates that continued participation in the study is not in the best interest of the participant
- Termination of the study by Bristol-Myers Squibb (BMS)
- Loss of ability to freely provide consent through imprisonment or involuntarily incarceration for treatment of either a psychiatric or physical (eg, infectious disease) illness
- Criteria listed in [Section 8.1.1](#)
- Disease recurrence or occurrence of a secondary malignancy which requires systemic therapy or radiotherapy for treatment

Refer to the Schedule of Activities for data to be collected at the time of treatment discontinuation and follow-up and for any further evaluations that can be completed.

In the case of pregnancy, the investigator must immediately notify the BMS Medical Monitor/designee of this event. In the event a normal healthy female participant becomes pregnant

during a clinical trial, the study treatment must be discontinued immediately. In most cases, the study treatment will be permanently discontinued in an appropriate manner (eg, dose tapering if necessary for participant safety). Please call the BMS Medical Monitor or designee within 24 hours of awareness of the pregnancy. If the investigator determines a possible favorable benefit/risk ratio that warrants continuation of study treatment, a discussion between the investigator and the BMS Medical Monitor/designee must occur.

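### The exploratory FKSI-19 and EQ-5D-3L comparisons with placebo use per-visit t-tests with the tested variable unnamed and no baseline covariate; a covariate would narrow the intervals by 8-13% against change-score t-tests (assumed correlation 0.7-0.5)

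*Combined protocol and SAP*

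**What the plan says.** Section 10.3.3.3 begins with descriptive summaries: "Mean changes from baseline for each of the 2 assessments and all associated subscores will be calculated for each treatment arm". It then adds the comparison with placebo: "Additionally, t-tests will be conducted to evaluate the differences between nivolumab combined with ipilimumab versus placebo infusions treatment arms". The sentence continues with nivolumab against placebo, at each time point, with 95% CIs. It names no tested variable and no covariate.

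Table 4-1 lists both endpoints as exploratory and defines both as changes: "Change in FKSI-19 subscale and total scores relative to baseline" and "Change in scores from baseline in EQ-5D-3L in both the visual analog scale and the utility index".

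The baseline form exists for both instruments. Table 2-2 has them "Completed on Day 1 of Cycles 1, 3, 6, 9, and 12 prior to any study-related procedures". Footnote c of that table allows FKSI-19 item GP5 to be left blank at Cycle 1 Day 1. After treatment, Table 2-3 continues the forms: "Perform at Follow-up 1 and 2, the first Survival Visit and at every other survival Follow-Up visit thereafter".

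For exploratory efficacy endpoints in general, Section 10.3.1 says of the methods: "Will be described in the statistical analysis plan finalized before database lock". Section 10.3.3.2 likewise leaves biomarker methods to the SAP. Section 10.3.3.3 contains no such deferral and states its own method.

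**The concern.** Two things are open. First, the t-test sentence leaves the analyst to choose between raw scores and changes. The choice recurs across eight scores (FKSI-19 total, four subscales, FKSI-DRS, EQ-5D utility and VAS), four post-baseline on-treatment visits and two comparisons: 8 x 4 x 2 = 64 tests before any follow-up visit is counted.

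Second, the plan makes limited use of a baseline score it already collects. A raw-score t-test ignores it. A change-score t-test subtracts it in full, which is a crude adjustment and is efficient only when the correlation is close to 1. Regressing on baseline lets the data set the weight. What is at stake is the width of the intervals around the quality-of-life differences, most of all in Part B, where the placebo arm has only about 200 participants.

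**Working it through.** **Plan's own figure.** There is none to reproduce. The documents give no SD, correlation, power or precision target for either questionnaire.

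**Inputs from the documents.** Part A: 400 vs 400 (Section 10.1.1). Part B, nivolumab vs placebo: 400 vs 200 (Section 10.1.2). Confidence level: 95% (Section 10.3.3.3).

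**Assumed.** Baseline-to-follow-up correlation r of 0.5 to 0.7, with 0.3 to 0.8 as a wider range; equal variance at both visits; complete forms unless stated.

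**Formulas**, in units of the score SD:
- Residual variance v: raw score 1; change score 2(1-r); baseline covariate 1-r².
- Half-width = 1.96 x sqrt(1/n1 + 1/n2) x sqrt(v).
- Width ratio, covariate to change: sqrt[(1-r²)/(2(1-r))] = sqrt[(1+r)/2]. Covariate to raw: sqrt(1-r²).

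**Width ratios.**
- r = 0.5: sqrt(0.75) = 0.866 against change, so 13% narrower; sqrt(0.75) against raw, also 13%.
- r = 0.7: sqrt(0.85) = 0.922 against change, so 8% narrower; sqrt(0.51) = 0.714 against raw, so 29%.
- r = 0.3 and 0.8: sqrt(0.65) = 0.806 and sqrt(0.90) = 0.949 against change, so 19% and 5% narrower.

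**Half-widths.** The multiplier 1.96 x sqrt(1/n1 + 1/n2) is 0.139 in Part A and 0.170 in Part B.

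| | r | raw | change | baseline covariate |
|---|---|---|---|---|
| Part A | 0.5 | 0.139 | 0.139 | 0.120 |
| Part A | 0.7 | 0.139 | 0.107 | 0.099 |
| Part B | 0.5 | 0.170 | 0.170 | 0.147 |
| Part B | 0.7 | 0.170 | 0.131 | 0.121 |

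Exact t quantiles and the lost degree of freedom move these by at most 0.001. A 1,500-run simulation of 400 vs 200 gave 13.3% and 7.7% against change, and 13.3% and 28.5% against raw. The percentages are the same at 70% completion. Against the change score, the gain equals 1/0.75 = 1.33 to 1/0.85 = 1.18 times the participants.

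**What the other visits add.** With complete forms, a joint model over visits has the same variance at Cycle 12 as single-visit ANCOVA (ratio 1.000). With an assumed 80% retained, the ratio is 0.960 to 0.976. The precision gain is therefore nearly all from the baseline covariate.

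**Why a joint model rather than visit-by-visit ANCOVA.** Six assumed scenarios were simulated with no true effect: 400 per arm, r of 0.5 to 0.7, per-visit dropout of 8% or 5% active against 3% placebo, depending on the preceding score. At Cycle 12 the bias in SD was -0.003 to -0.042 for the change-score t-test and +0.007 to +0.071 for single-visit ANCOVA. It was within 0.003 of zero for a joint likelihood estimate (sequential regressions standing in for the mixed model).

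**The case against.** The strongest reply is that nothing is broken. The t-test is valid under randomization, the endpoints are exploratory, and no precision target is missed. In absolute terms the gain over a change score is 0.008 to 0.023 SD (0.107 - 0.099 in Part A at r = 0.7; 0.170 - 0.147 in Part B at r = 0.5). Every correlation is assumed. Table 4-1 and the preceding sentences of Section 10.3.3.3 make change from baseline the natural reading. The SAP may already contain a model. All of this stands and limits the point to a minor one. It does not remove the gain, which under equal variances is positive for any correlation below 1.

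A second reply is that the headline gain comes from the covariate, while visit-by-visit ANCOVA did worse than the change-score t-test under score-dependent dropout. That is correct, and it is why the recommendation is the joint model. The model in turn relies on missing-at-random dropout and, at the treatment cycles, estimates the difference had on-treatment forms continued.

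A reader might infer that the plan ignores baseline altogether. It does not if changes are tested, since a change score already subtracts baseline. A reader might also infer that forms simply stop when treatment stops and that the t-tests are biased for that reason. The documents do not support that: "Participants who request to discontinue study treatment will remain in the study and must continue to be followed for protocol specified follow-up procedures" (Section 8.1), and both forms are scheduled at follow-up visits. The simulated change-score bias was small and rests on invented dropout rates.

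**Conclusion.** The point holds as a minor, cheap improvement. The t-test sentence should name its variable, and a baseline covariate would narrow the intervals by 13% to 8% against change-score t-tests for r of 0.5 to 0.7 (19% to 5% for 0.3 to 0.8), or by 13% to 29% against raw-score t-tests for r of 0.5 to 0.7. These figures rest on an assumed correlation and equal variances.

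It would be wrong to conclude that the planned tests are invalid, that any quality-of-life conclusion would change, or that DFS, OS or the adverse-event safety analyses are touched. It would also be wrong to say that the trial has no such model: the protocol text has none, but the SAP text was not available to check.

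**What to change.** In Section 10.3.3.3 or the SAP:

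- State that change from baseline is analysed, in line with Table 4-1.
- Within each Part, estimate the arm differences from a repeated-measures model with treatment, visit, treatment-by-visit, baseline score and baseline-by-visit, and report per-visit differences with 95% CIs.
- Apply the same baseline covariate to the scheduled follow-up forms, so that no planned time point is left unadjusted. Keep the t-tests as supportive.
- Fix one FKSI-19 scoring rule for the possibly blank GP5 item at baseline. A change score needs this too.
- If the SAP already specifies such a model, cross-reference it instead.

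The cost is a few sentences and a little programming, with no new data, plus the reliance on missing-at-random dropout. The change must be labelled post hoc for any Part already unblinded. That may apply to Part A: the Amendment 05 rationale in Appendix 8 projected its final DFS event count within about 4 months of the interim count in early 2022, and this version is dated December 2022. Amendment 06 still treats the timing of the Part B DFS analyses as ahead, so Part B can probably be pre-specified.
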